### 9 STUDY PROCEDURES

Table 5 outlines the timing of procedures and assessments to be performed throughout the study. See Section 9.1 for additional details of study procedures.

17 June 2020 Page 59 of 110

Table 5: Schedule of Assessments

Month	-1 -4		0	1		2		3	6	9	12	13
Week			0	2 4		6	8	12	24	36	48	52
Visit window	+ 2 weeks		0	± 3 days	± 3 days	±3 days	± 3 days	± 7 days	± 7 days	± 7 days	± 7 days	± 7 days
	Vl	V2	V3	V4	V5	V6	V7	V8	V9	V10	V11	V12
Visit*	Screening		Rand								EOS/Early Withdrawal 	FUV 
Informed consent	X											
Eligibility criteria	X											
Medical history and demographic data	X											
Prior and concomitant medications	Х		X	Х	X		X	X	X	X	Х	x
Physical examination	X		X	X	X		X	X	X	X	X	X
Vital Signs	X		X	X	X		X	X	X	X	X	X
Weight	X		X	X	X		X	X	X	X	X	
Height	X										X	
ECG Test 	X		X	X	X		X	X	X	X	X	X
ЕСНО	X										X	
Pulmonary function tests 	X										X	
Serology 	X											
Hematology 	X		X	X	X	X	X	X	X	X	X	X
Blood chemistry 	X						X	X	X	X	X	X
Thyroid function tests (TSH, fT3, fT4)	X				x		x	x	X	X	X	x
Coagulation tests (PT and aPTT)	X						X	X	X	X	X	X
Urine analysis 	X						X	X	X	X	X	X
SF-36	X		1								X	
Time function tests (time to climb 4 standard steps, time to rise from floor, time to walk 10 m)	х							х	х	х	x	

17 June 2020 Page 60 of 110

Month	-1		0	1		2		3	6	9	12	13
Week	-4		0	2	4	6	8	12	24	36	48	52
Visit window	+ 2 weeks		0	± 3 days	± 3 days	±3 days	± 3 days	± 7 days	±7 days	± 7 days	± 7 days	± 7 days
	Vl	V2	V3	V4	V5	V6	V7	V8	V9	V10	V11	V12
Visit*	Screening		Rand								EOS/Early Withdrawal 	FUV 
6MWT	X		X					X	X	X	X	
MFM	X							X	X	X	X	
Muscle strength 	X							X	X	X	X	
PK blood sample collection 					X			X	X		X	
Biomarkers blood collection 			X						X		X	
Study treatment dispensation and accountability			Х					X	X	X		
Patient diary dispensation			X									
Patient compliance through diary								X	X	X	X	
AE assessment	X	X	X	X	X	X	X	X	X	X	X	X
MR + Muscular biopsy		$X^{11}$									$X^{13}$	

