6MWT=6-minute walking test; AE=adverse event; MFM= Motor Function measure; SF36= Short Form (36) Health Survey; PT=Prothrombin time; aPPT= activated partial thromboplastin time; ECG= electrocardiogram; ECHO= echocardiogram; PK= pharmacokinetics; MRI= magnetic resonance imaging; FEV1= forced expiratory volume at 1 second; FVC=forced vital capacity; PEF= peak expiratory flow; RBC-red blood cell; WBC=white blood cell; ALT=alanine aminotransferase; AST=aspartate aminotransferase; LDH= lactate dehydrogenase; CRP=C-reactive protein; GGT=gamma-glutamyl transpeptidase; BUN=blood urea nitrogen; fT3= free T3 (the active part of triiodothyronine); fT4=Free T4 (the active part of thyroxine); TSH=thyroid-stimulating hormone; eGFR=estimate Glomerular Filtration Rate; HHM=hand-held myometry; MMT=manual muscle testing

- \* Unscheduled visits may take place at the discretion of the Investigator such as additional cardiology visits at the study center or visits at the patient's home by a qualified trained nurse for blood sample collection.
- If the patient is discontinued from the study treatment, the patient will be asked to return for the early withdrawal visit to be performed within 4 weeks
  of the last dose of study treatment. In this case, the SF-36 evaluation and MRI may not be performed.
- The patients who complete the study (i.e. 12 months of treatment) will be asked to return to the centre for the Follow-up visit to be performed after 4
  weeks from the last dose of study treatment (i.e. 4 weeks ±1).
- 3. A 12-lead ECG is to be done in triplicate at the screening visit and during the other visits if an ECG demonstrates a prolonged QTcF interval > 450 msec obtained on 2 more ECGs over a brief period. The averaged QTcF values of the 3 ECGs is to be used to determine whether the patients should be discontinued from the study.
- Pulmonary function tests: FEV1, FVC and PEF.
- Serology CMV IgM, HBsAg/HCV/HIV, EBV IgG.

17 June 2020 Page 61 of 110

- 6. Hematology test: RBC, WBC (including differential count), hemoglobin, MCH, MCHC, MCV, hematocrit, and platelets. Test will be done according to the schedule (i.e., every two weeks the first 2 months of treatment) and are to be performed more frequently if clinically indicated. Note: Repeat visits for the platelets count will be performed at the request of the Investigator.

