## 9.1.10 Visit 11: End of Study Visit (EOS, Week 48 ± 7 days) and early withdrawal visit

The EOS (Visit 11) will be scheduled at the end of treatment (i.e., 48 weeks after the Randomization Visit,  $\pm$  7 days). Patients will be instructed to take the morning dose at the site in case of pre-dose PK analysis.

Patients who prematurely withdraw from the study for any reason will undergo an Early Withdrawal Visit within four weeks after the last dose of study treatment. The Early Withdrawal Visit requirements are the same as those of the EOS Visit described in this section.

The following assessments will be performed during this visit:

- Concomitant medications
- Physical examination
- Vital signs (blood pressure, heart rate and body temperature)
- Weight
- Height
- 12-lead ECG
- Echocardiogram
- Pulmonary function tests: FEV1, FVC, FEV1/FVC, and PEF
- Blood collection for
  - hematology
  - blood chemistry
  - coagulation tests (PT and aPTT)
  - thyroid function tests (TSH, fT3, fT4)
  - PK analysis
  - Biomarker analysis
- Urine analysis;
- 6MWT + MFM
- Muscle strength test (knee extension and elbow flexion by HHM)
- Timed function tests
- Quality of Life test (assessed by SF-36)
- AE assessments

17 June 2020 Page 68 of 110

- Diary return and patient compliance
- MRI/MRS and muscle biopsy evaluations, which may be performed on different days (in case of early withdrawal visit the MRI/MRS and Quality of Life test do not have to be performed). Treatment is to continue up to the last assessment.

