3. BACKGROUND AND RATIONALE

3.1. Overall Study Design and Plan Description

This is a phase 2, randomized, double-blind, placebo-controlled study. Ambulant patients who have provided written informed consent will undergo a 4-week screening period to determine eligibility for the study. Approximately 51 eligible patients will then be randomized in a 2:1 ratio to be treated with givinostat or placebo for a period of 12 months. The randomization process will be stratified by the factor related to the concomitant steroids use at baseline (yes vs. no). Patients who complete the study (i.e. 12 months of treatment) will be asked to return for a follow-up visit 4 weeks after the end of treatment.

An overview of the study is provided in Figur.

Figure 1: Study Design

Sponsor: ITALFARMACO
Protocol: DSC/15/2357/53

A total of 12 visits will take place during the study: Screening (V1, V2), Randomization (V3), Treatment (V4-V10), End of Study (V11) and Follow-up (V12). Visits during the treatment period will take place every 12 weeks except for the first 2 months, when they will occur every 2 weeks to allow close monitoring of hematological safety parameters. Patients may be evaluated more often if necessary, for safety reasons. Patients who discontinue the study treatment early will be asked to come in for an Early Withdrawal Visit within 4 weeks after the last dose of study treatment. Patients who have ongoing AEs at discontinuation will be followed until resolution or stabilization.

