6.3.1. Primary efficacy analysis

Definition of primary endpoint

The primary endpoint is the mean change in total fibrosis comparing the histology of muscle biopsies before and after 12 months of treatment with givinostat versus placebo. The primary efficacy assessment for this study is the Total Fibrosis assessed through histological examination of muscle biopsies. A muscle biopsy was collected at the beginning and at the end of treatment to calculate the mean change from baseline to 12 months.

For each patient, the percentage of total fibrosis will be calculated as a mean of available fields at each evaluation.

Analysis methodology

The primary hypothesis to be tested is that total fibrosis (%) will increase less in the givinostat group than in the placebo group.

Since the blinded data at the time of the sample size re-estimation indicated the primary efficacy variable to be non-Normally distributed, the change in mean fibrosis from baseline to endpoint after 12 months of therapy will be analyzed on the log scale. Therefore, mean fibrosis at baseline and Visit 11 will be log transformed prior to analysis. An analysis of covariance (ANCOVA) model will be fitted to the data with the difference between log visit 11 and log baseline values as the dependent variable; log baseline value will be included as covariate and treatment and concomitant steroid use at baseline as independent class variables. LSmean values for the log change from baseline to visit 11 will be extracted, together with the associated log scale SEs; the difference in LSmean values will also be extracted as the measure of treatment effect along with corresponding log scale SE and two-

Sponsor: ITALFARMACO
Protocol: DSC/15/2357/53

sided 95% Confidence Interval (CI). LSmean values, the difference in LSmean values and the associated CI will be back transformed to the ratio scale for the purpose of presentation.

Summary descriptive statistics (N, geometric mean, %CV, mean, median, SD, min and max) for total fibrosis value and change versus baseline, at each time point, will be provided.

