A Mixed Model will be fitted to the data with the difference between log visit 11 and log baseline values as the dependent variable; log baseline as a covariate, treatment will be included as independent class variables and treatment by sequence interaction. The sequence of biopsy site (Right-Left, Left-Right) will be included as a fixed effect and subject as a random effect to evaluate the difference in Total Fibrosis between biopsy sites.

If the treatment by sequence interaction is p>0.10, then the model without the interaction term will be presented.

Data handling rules

Primary analysis will be based on observed data only.

Sensitivity analysis for the primary endpoint will be performed as follow:

- 1. Multiple imputation for missing data:
 - a. Missing baseline primary endpoint data will be imputed as the geometric mean of all non-missing baseline primary endpoint values across the randomized treatment groups. Visit 11 missing data will be imputed (on the log scale) under a Missing At Random (MAR) assumption using SAS procedure MI within each treatment group using distribution implied by the non-missing patient data for that treatment group. A total of 20 imputation runs will be performed. Post imputation, each imputed dataset will be analysed separately exactly as described for primary efficacy analysis. The SAS procedure MIANALYZE will then be used to combine the 20 datasets of estimates by Rubin's rules. The resulting multiply imputed means and difference in means will be presented, along with the associated SEs, 2-sided 95% CIs and 2-sided p-values.
 - b. Missing baseline primary endpoint data will be imputed as the geometric mean of all non-missing baseline primary endpoint values across the randomized treatment groups. Visit 11 missing data will be imputed (on the log scale) under a Missing Not At Random (MNAR) assumption using SAS procedure MI for both randomized treatment groups using the distribution implied by the non-missing patient data within the placebo group. A total of 20 imputation runs will be performed. Post imputation, each imputed dataset will be analysed separately exactly as described for primary efficacy analysis. The SAS procedure MIANALYZE will then be used to combine the 20 sets of estimates by Rubin's rules. The

Sponsor: ITALFARMACO
Protocol: DSC/15/2357/53

resulting multiply imputed means and difference in means will be presented, along with the associated SEs, 2-sided 95% CIs and 2-sided p-values.

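### Does the primary analysis need a rule for muscle biopsies taken at early withdrawal?

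*SAP*

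**What the plan says.** **Protocol.** The V11 column of Table 5 is headed "EOS/Early Withdrawal". Section 9.1.10 places Visit 11 at 48 weeks ± 7 days and adds: "The Early Withdrawal Visit requirements are the same as those of the EOS Visit described in this section". The exemptions are narrow. Table 5 footnote 1 says "In this case, the SF-36 evaluation and MRI may not be performed", and section 9.1.10 says "in case of early withdrawal visit the MRI/MRS and Quality of Life test do not have to be performed". Neither names the biopsy. Section 7.3.1 also sends patients stopped under the safety rules to the EOS visit.

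**SAP.** Section 6.3.1 describes the data this way: "A muscle biopsy was collected at the beginning and at the end of treatment to calculate the mean change from baseline to 12 months". The ANCOVA is fitted "with the difference between log visit 11 and log baseline values as the dependent variable", and the data rule is "Primary analysis will be based on observed data only". Section 4.4.3 includes drop-outs in each analysis with whatever assessments they have. Section 3.1 lists V11 as End of Study and describes the Early Withdrawal Visit separately. Sensitivity analyses 1a (missing at random, within arm) and 1b (missing not at random, from placebo) impute missing values. Sensitivity analysis 3 repeats the primary analysis on the Per Protocol Set, whose exclusions sit in a separate document.

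**The concern.** The protocol plans for early biopsies and files them under the visit that the primary model uses. The SAP gives no analysis window. Read literally, a biopsy at week 10 could enter as a 12-month change, and SAP 6.3.1 treats end of treatment and 12 months as the same moment, which is untrue for anyone who stops early.

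The multiple imputations would not expose this. They act only on missing values, so an early biopsy that counts is left alone, and one that does not count is never used.

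At stake would be a primary estimate mixing full-year and shorter changes. If fibrosis rises in both arms and more givinostat patients stop, the mix favours givinostat. If fibrosis falls on drug, as in the DMD study in Protocol 4.2.2, it hides benefit.

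**Working it through.** **1. The plan's own figure.** Inputs (Protocol 13.1): difference 9 points, SD 10, two-sided 5%, 2:1. The two-sample t-test gives 82.1% power at 32 + 16 and 79.4% at 30 + 15, so 48 is the smallest 2:1 total reaching 80%. Then 48/0.95 = 50.5, rounded up to 51 (34 + 17). Both figures reproduce. The 5% allowance is for unevaluable biopsies, not withdrawals.

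**2. The two readings.** For counting: the shared V11 column and SAP 4.4.3. Against counting: the 12-month endpoint, Week 48 ± 7 days, and the separate Early Withdrawal Visit in SAP 3.1. Under the second reading an early stopper's Visit 11 value is missing, and 1a and 1b already cover it.

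**3. Bias if early biopsies count.** Assumed, since the documents give no rates: no drug effect, log-linear progression with yearly ratio R, biopsy at week t, residual log SD 0.33. With p_G and p_P the stopping proportions on givinostat and placebo,

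log bias = −ln(R) × (1 − t/48) × (p_G − p_P).

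For t = 10, 1 − 10/48 = 0.7917. With stopping on givinostat only:

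| R | Stopping | Log bias | Ratio | Simulated ratio | Type I error |
|---|---|---|---|---|---|
| 1.30 | 5% | −0.2624 × 0.7917 × 0.05 = −0.0104 | 0.990 | 0.989 | 5.0–5.1% |
| 1.30 | 15% | −0.0312 | 0.969 | 0.969 | 5.7–6.0% |
| 1.30 | 30% | −0.0623 | 0.940 | 0.940 | 8.9–9.3% |
| 1.20 | 30% | −0.1823 × 0.7917 × 0.30 = −0.0433 | 0.958 | 0.959 | 6.9% |
| 1.10 | 30% | −0.0953 × 0.7917 × 0.30 = −0.0226 | 0.978 | 0.979 | 5.5% |

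With p_G = p_P the bias is zero (simulated type I error 5.0–5.2%).

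A milder case has 15% against 5% stopping, spread evenly over the year (mean share missed 0.5). At R = 1.30 the log bias is −0.2624 × 0.5 × 0.10 = −0.0131, ratio 0.987. The standard error is about 0.33 × √(1/34 + 1/17) = 0.098, so the bias is 0.0131/0.098 = 0.13 standard errors.

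**4. Bias if they do not count.** If stopping is unrelated to outcome, setting early biopsies to missing gives a ratio of 1.00. Now let the stopping tendency correlate ρ = 0.5 with the residual change, so that patients with larger rises tend to stop. The givinostat patients who remain then have mean residual −ρ × 0.33 × φ(z)/(1 − w), where w is the share stopping and z the matching normal cut-off.

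- w = 0.15: 0.5 × 0.33 × 0.233/0.85 = 0.0453, ratio 0.956, against 0.969 if kept.
- w = 0.30: 0.5 × 0.33 × 0.348/0.70 = 0.0820, ratio 0.921, against 0.939 if kept.

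Imputing them does not settle it (simulated, at 15% and 30%). With early biopsies set to missing, 1a gives 0.957 and 0.918, and 1b gives 0.965 and 0.947. With them kept, 1a gives 0.970 and 0.939, and 1b gives 0.972 and 0.942. The best choice changes with the scenario.

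**5. Effect on power.** Difference 9, SD 10, change accruing linearly, biopsy at fraction f of the year:

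| Early stoppers (givinostat + placebo) | Not counted | Counted, f = 0.1 | f = 0.25 | f = 0.5 | f = 0.75 |
|---|---|---|---|---|---|
| 2 + 1 | 82.1% | 80.3% | 81.0% | 82.2% | 83.3% |
| 6 + 3 | 76.5% | 70.5% | 73.1% | 77.3% | 81.0% |

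Counting dilutes the difference (for 2 + 1 at f = 0.1, to 9 × (1 − 0.0588 × 0.9) = 8.52) but keeps patients. Very early biopsies cost power and late ones add it.

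**6. The planned analyses on one simulated trial** (6 + 1 early biopsies, illustrative values, log scale). Counted, with nothing else missing: observed-data, 1a and 1b all give −0.2416. Not counted: −0.2507, −0.2413 and −0.2164. The imputations indeed take the classification as given. In this example the two observed-data estimates differ by 0.2507 − 0.2416 = 0.0091, against a standard error of 0.0908 when counted.

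**The case for a change.** The strongest case for a change is that two defensible readings of the primary variable remain in a 51-patient trial, and a sentence written before unblinding would remove a post-hoc choice. Platelet reduction is a known drug effect with permanent-stop thresholds (Protocol 7.3.1), so unequal stopping is plausible, and drop-outs are not replaced (section 7). Amendment 4 gave up LOCF for this endpoint as questionable and not conservative. Under linear progression a week-10 biopsy used as month 12 carries 1 − 10/48 = 79% of the bias of a baseline carried forward (50% at week 24, 25% at week 36).

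Part of this stands. The SAP has no timing rule, and 1a and 1b cannot compare the readings. At 15% and 30% one-sided stopping unrelated to outcome, with biopsies kept, they give 0.965 and 0.940 (1a) and 0.967 and 0.942 (1b), which would seem to confirm the primary result.

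The rest is weaker. Amendment 4 objected to substituting the baseline for a missing value, whereas an early biopsy is an observed post-treatment measurement. Protocol Amendment No. 2 reports 11 of 21 dose reductions and three temporary interruptions at the higher starting dose then in use, and mentions no permanent stop. Unequal stopping would be visible: Protocol 13.3 tabulates discontinuations and reasons by arm, and SAP 6.4.1 summarises exposure by arm. The Per Protocol repeat may also remove early stoppers, though its exclusions cannot be checked here.

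The move of multiple imputation from the protocol's primary analysis to the SAP's sensitivity analyses is a separate matter. SAP 1.1 discloses it. The missing rationale and the loose wording of sensitivity analysis 2 are clerical.

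**Conclusion.** No change follows. SAP 6.3.1 omits a detail that analysts can fill from the 12-month endpoint and the Week 48 ± 7 days timing of Visit 11. The choice is also a fair trade-off. Keeping early biopsies brings in a timing bias when stopping is unequal; dropping them brings in a selection bias when stopping is related to outcome, and it costs patients. A written rule would record a choice without making the estimate reliably better, and under the 12-month reading 1a and 1b already treat these patients as missing.

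The effect is negligible at 5% one-sided stopping (ratio 0.99), small at 15% (0.97), and absent with equal stopping and no drug effect. It becomes material (0.94, type I error about 9%) only if some 30% of givinostat patients and no placebo patients stop, all are biopsied at week 10, and fibrosis rises 30% a year. None of those inputs is in the documents. The conclusion would weaken if permanent stopping proved both common and clearly unequal between arms.

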6.3.2. Secondary efficacy analysis

6.3.2.1. Magnetic Resonance Spectroscopic (MRS)

Definition

MRS variables will include:

- Fat Fraction in the vastus lateralis muscles
- Fat Fraction in the soleus

Analysis methodology

The absolute value of fat fraction of vastus lateralis and change versus baseline, at each time point, will be summarized as a continuous variable using descriptive statistics.

The absolute change in fat fraction of vastus lateralis after 12 months of therapy, as assessed by MRS, will be analyzed using an ANCOVA model with baseline fat fraction of vastus lateralis value as covariate and treatment and concomitant steroid use at baseline as independent class variables.

Possible need for log transformation of this variable will be assessed by check of ANCOVA model residuals. If considered non-Normal, a supportive analysis will be performed on the log scale.

The same analyses will be done for the fat fraction of soleus.

Data handling rules

The analysis will be based on observed data only.

6.3.2.2. Magnetic Resonance Imaging (MRI)

Definition

MRI variables will include:

Sponsor: ITALFARMACO Protocol: DSC/15/2357/53

- Fat Fraction (%) in the lower limb muscles (i.e. whole thigh, quadriceps, medial Thigh, Hamstrings, Triceps surae muscles and Pelvis Girdle)
- Cross-sectional area and contractile area in the lower limb muscles (i.e. whole thigh, quadriceps, medial Thigh, Hamstrings, Triceps surae muscles and Pelvis Girdle)

Analysis methodology

The absolute value of fat fraction of lower limb muscles and change versus baseline, at each time point, will be summarized as a continuous variable using descriptive statistics.

The absolute change in fat fraction of lower limb muscles after 12 months of therapy, as assessed by MRI, will be analyzed using an ANCOVA model with baseline fat fraction of lower limb muscles value as covariate and treatment and concomitant steroid use at baseline as independent class variables. Possible need for log transformation of this variable will be assessed by check of ANCOVA model residual. If considered non-Normal, a supportive analysis will be performed on the log scale.

The absolute value of Cross-sectional Area (CSA) and contractile area of lower limb muscles and change versus baseline, at each time point, will be summarized as a continuous variable using descriptive statistics.

The absolute change in CSA and contractile area of lower limb muscles after 12 months of therapy, as assessed by MRI, will be also analyzed using an ANCOVA model with baseline CSA and contractile area of lower limb muscles value as covariate and treatment and concomitant steroid use at baseline as independent class variables. Possible need for log transformation of this variable will be assessed by check of ANCOVA model residual. If considered non-Normal, a supportive analysis will be performed on the log scale.

Data handling rules

Primary analysis will be based on observed data only.

Sensitivity analyses for the MRI endpoints will be performed as follow:

- 1. Multiple imputation for missing data:
 - a. Missing baseline primary endpoint data will be imputed as the mean of all non-missing baseline primary endpoint values across the randomized treatment groups. Visit 11 missing data will be imputed under a Missing At Random (MAR) assumption using SAS procedure MI within each treatment group using distribution implied by the non-missing patient data for that treatment group. A total of 20 imputation runs will be performed. Post imputation, each imputed dataset will be analysed separately exactly

Sponsor: ITALFARMACO
Protocol: DSC/15/2357/53

as described for primary efficacy analysis. The SAS procedure MIANALYZE will then be used to combine the 20 datasets of estimates by Rubin's rules. The resulting multiply imputed means and difference in means will be presented, along with the associated SEs, 2-sided 95% CIs and 2-sided p-values.

b. Missing baseline primary endpoint data will be imputed as the mean of all non-missing baseline primary endpoint values across the randomized treatment groups. Visit 11 missing data will be imputed under a Missing Not At Random (MNAR) assumption using SAS procedure MI for both randomized treatment groups using the distribution implied by the non-missing patient data within the placebo group. A total of 20 imputation runs will be performed. Post imputation, each imputed dataset will be analysed separately exactly as described for primary efficacy analysis. The SAS procedure MIANALYZE will then be used to combine the 20 sets of estimates by Rubin's rules. The resulting multiply imputed means and difference in means will be presented, along with the associated SEs, 2-sided 95% CIs and 2-sided p-values.

